5.1.4.3 Transplantation Phase

At the end of any organ offer from a deceased donor, per usual transplant center practice, the investigator will discuss with the subject characteristics of the allograft and risks and benefits presented by transplantation using that allograft, and the subject can accept or reject that allograft.

A kidney transplantation event will prompt a shift to the “transplantation phase.” The elements of the transplantation phase will depend on the type of kidney transplant. Subjects who undergo transplantation with a study-eligible HCV RNA-negative/HCV Ab-positive in Arm 2A will be followed as per standard of care, and with surveillance of HCV RNA as per Figure 1b, and outcomes of G/P treatment collected up to 1 year post transplant if applicable and according to Table 6 and Section 5.1.5.2.

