Day 1 of G/P treatment	V3	✓	✓								✓	✓	✓	✓	✓				
Treatment week 1 ±3 days	V4	✓	✓		✓			✓					✓	✓	✓				
Treatment week 2 ±3 days	V5 T5	✓	✓		✓														
Treatment week 4 ±3 days	V6	✓	✓		✓	✓		✓			✓	✓	✓	✓	✓	✓			
Treatment week 6 ±3 days ¹⁰	T7	✓	✓		✓														
Treatment week 8 ±7 days (EOT)	V8	✓	✓		✓			✓			✓		✓	✓	✓				
Post treatment week 4 ±7 days	V9 T9	✓	✓																
Post treatment week 12 ±14 days	V10	✓	✓					✓	✓										
Post treatment week 24 ±28 days	V11	✓	✓					✓	✓				✓	✓	✓				
1 year Post transplant ±28 days; End of study ¹¹	V12	✓	✓					✓	✓				✓	✓	✓				
G/P treatment failure		✓						✓	✓	✓									
Premature discontinuation		✓						✓	✓	✓			✓	✓	✓				

1 Visit types: V - in person visit to site; L - Lab visit; T - Telephone encounter

2 Includes evaluation of blood type and HLA compatibility

3 HCV RNA testing at V2, V4, V8, and V10 and V11 are study paid labs. HCV RNA testing at visit 6 is billed as SOC. All HCV RNA testing is done at local laboratory by a CLIA certified laboratory and with an FDA approved test.

4 Archived plasma samples (required) and PBMC (optional at Visits 8, 10, and 12) samples are shipped to the clinical coordinating center at Massachusetts General Hospital, see section 5.3.1.1

5 Lack of availability of donor blood sample will not preclude donor eligibility or transplant. HCV genotype is determined from the donor blood sample at local laboratory; Another portion of the donor sample is frozen for storage and potential testing for DAA resistance as needed. See section

5.3.1.1

6 If visit 2 and visit 3 are on the same day or within 14 days of each other only 1 serum pregnancy test need to be obtained. Visit 6 and Visit 8 pregnancy tests can be urine tests. Additional pregnancy tests not billed to the study are obtained as per transplant center standard of care.

7 Vitals and physical exam will be conducted and documented as per standard of care at transplant center

8 Liver function tests (ALT, AST, Alk Phos., total bilirubin) will be ordered as a study lab if not standard of care as part of clinical chemistry labs at the local transplant center. See table 8 for clinical chemistry labs and hematology labs.

9 Includes Tacrolimus level and/or other utilized immunosuppressant that requires therapeutic drug monitoring as per transplant center standard of care;

10 Telephone call will be performed between clinic visits at treatment week 6 to assess subject adherence to G/P treatment.

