5.1.9 Additional Visits

Additional visits will only be necessary in the case of G/P treatment failure of subjects who received an HCV RNA-positive kidney. After treatment failure has been confirmed, a suitable retreatment regimen will be provided by the MYTHIC study. The retreatment regimen will be chosen at the discretion of the overall PI, [name] with input from the site investigator. The retreatment of study subjects, however, will be followed by the site investigator and as per local center standard of care. The following information of standard-of care visits for retreatment of a subject who failed G/P in this study will be obtained: Any SAE and relatedness of SAE to retreatment regimen from the 1st dose of retreatment regimen to 30 days post last dose of retreatment regimen; Any retreatment regimen emergent laboratory abnormality \geq Grade 3 until 2 days post last dose of retreatment regimen; any early discontinuation of retreatment regimen, reason for not achieving SVR12; HCV plasma RNA before start of re-treatment regimen and 12 weeks after end of re-treatment.

5.1.10 Schedule of events for patients who receive no transplant or standard of care kidney transplant

Enrolled subjects who undergo a standard of care kidney transplant or who remain on the transplant waiting list will have limited study visits and procedures. These subjects will be followed for a minimum of 1 year post enrollment if they did not receive a transplant during that time. Subjects who received a standard of care kidney transplant will be

followed for 24 weeks post transplant or a minimum of 1 year post enrollment, whichever is longer.

After enrollment and while on the waiting list, there will be telephone contacts with study subjects every two months to ascertain interim events of importance to protocol-data collection, including non-SAE hospitalizations, SAEs, change in wait list status. For those who have a standard of care kidney transplant, death, graft failure, acute allograft rejection, delayed graft function ALT elevation > 5x ULN, eGFR, proteinuria (as available) and SAEs will be obtained from the subject's medical record. eGFR will be measured at each standard of care clinic visit, with particular focus on the 6-month visit. These data will be entered into study eCRFs.

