6.1.8. Management of ALT elevations while on study drug G/P

If a subject experiences a post-baseline increase in ALT to $> 5 \times \text{ULN}$ which is also $> 2 \times$ baseline value, the subject should have a confirmatory ALT measurement performed.

If the ALT increase is confirmed to be $> 5 \times \text{ULN}$ which is also $> 2 \times$ baseline value, the recommendations below should be followed:

- Evaluate for alternate etiology of ALT elevation; document in the source, update the medical history and concomitant medications eCRF (if applicable), and obtain additional testing as appropriate (e.g., hepatitis B panel).
- Manage the subject as medically appropriate.
- Repeat ALT, AST, total and fractionated bilirubin, alkaline phosphatase and INR within 1 week. Repeat liver chemistries as indicated until resolution.
- Discontinue study drugs if any of the following is observed at any time:
 - ALT level is $\geq 20 \times \text{ULN}$ in the absence of an alternate etiology.
 - Increasing direct bilirubin or INR or onset of symptoms/signs of hepatitis.

At the discretion of the investigator alternate management of ALT increases is permitted with approval of the Principal Investigator ([name]) at MGH.

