Clinical outcomes post-transplant will include death, graft failure, acute allograft rejection, delayed graft function, ALT elevation > 5 times the upper limit of normal, and SAEs. In addition, HCV-infection related events of fibrosing cholestatic hepatitis and extrahepatic manifestations of HCV infection collected for Arm 1 subjects and only for Arm 2A subjects who develop HCV viremia will also count as clinical outcomes. The number and percentage of subjects with each and any clinical outcomes will be summarized for those who receive an HCV RNA-positive kidney (Arm 1) versus Arm 2 subjects combined and broken down (2A and 2B) as applicable. The difference in the overall percentage of subjects with clinical outcomes post-transplant in Arm 1 vs Arm 2A + 2B will be assessed by logistic regression with Arm as a factor and including appropriate covariates to adjust for possible differences between Arms including waiting list priority, blood group,

geographic region and sensitization, as appropriate given sample size and other statistical considerations. In addition, to include any clinical outcomes due to being treated with G/P, another summary of clinical outcomes post-transplant will include any study drug (G/P) related severe treatment emergent adverse events for Arm 1 subjects, and another will include events of treatment emergent Grade ≥ 3 laboratory values and related severe treatment emergent adverse events as clinical outcomes for Arm 1 subjects.

Analyses of the eGFR outcome will be calculated eGFR using the 4-variable MDRD equation. Mean (SD) eGFR will be summarized at appropriate visits and compared between Arms. Specifically, mean eGFR at 24 weeks/6-months post-transplant and 1 year post transplant will be compared between Arm 1 transplant recipients and the combined group of Arm 2A and 2B transplant recipients (2B1-2B4). As a secondary approach, mean eGFR at 24 weeks/6-months post-transplant will be compared between Arm 1 recipients and Arm 2A and 2B kidney recipients limited to those 2A and 2B recipients who did not develop HCV infection.

We will also compare estimated proteinuria between Arms 1 and 2A, including a count of individuals with >1000 mg/day estimated proteinuria. Proteinuria will be estimated using spot protein:Cr ratio.

An exploratory analysis will summarize the number and percentage of subjects with clinical outcomes post kidney transplant for the subgroups of Arm 2B.

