13	Arm 1	Acute allograft rejection	AAR: Binary (0/1) response. Compute OBS/EXP, where OBS=observed number of AARs for Arm 1 and EXP= expected cunt based on logistic regression model fitted to HCV-negative UNOS patients from large academic centers
14	Arm 1	ALT elevation	Binary (0/1), with '1' corresponding to peak ALT > 5 x ULN, where ULN=upper limit of 'normal'.
15	All, by arm	Serious Adverse Event	SAE: recurrent event Arm treated as a time-dependent factor Proportional rates model, robust SEs to account for within-patient clustering
16	Arm 1, 2AB	eGFR	Repeated continuous response Linear mixed model, to account for clustering by patient
17	Arm 1, 2AB	Proteinuria	Binary response; logistic regression
18	Arm 1, 2AB	BK virus	Binary response; logistic regression

Notes:

a) Each of the above-listed analyses will be accompanied by appropriate summary statistics (e.g., mean, median, IQR, etc).

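### The post-transplant composite compared between arms includes ALT > 5x ULN, but liver tests are guaranteed on a schedule only in Arm 1; the bias runs against Arm 1 and is probably small in the composite

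*Protocol*

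**What the plan says.** **The comparison.** Protocol Section 8.1.4 counts death, graft failure, "acute allograft rejection, delayed graft function, ALT elevation > 5 times the upper limit of normal, and SAEs" as post-transplant clinical outcomes. Each outcome, and any outcome, is summarised by arm. Then the "difference in the overall percentage of subjects with clinical outcomes post-transplant in Arm 1 vs Arm 2A + 2B will be assessed by logistic regression". The named covariates are waiting list priority, blood group, geographic region and sensitization. The Synopsis repeats the comparison for Arms 2A + 2B1-2B4.

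**ALT in Arm 1.** Table 5 schedules clinical chemistry at the peri-transplant visit, day 3, G/P Day 1 and treatment weeks 1, 4 and 8, and again later. Footnote 8 adds a guarantee: "Liver function tests (ALT, AST, Alk Phos., total bilirubin) will be ordered as a study lab if not standard of care". Section 6.1.8 adds that after a rise on G/P "the subject should have a confirmatory ALT measurement performed", with further repeats if it is confirmed.

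**ALT in Arm 2A.** Under Section 5.1.4.3 these recipients "will be followed as per standard of care, and with surveillance of HCV RNA as per Figure 1b". The visit descriptions in Section 5.1.7 ask whether ALT exceeded 5x ULN but name no liver panel, and Table 6 has no counterpart to footnote 8.

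**ALT in Arm 2B.** Section 5.1.10 lists ALT > 5x ULN with the other outcomes and ends: "eGFR, proteinuria (as available) and SAEs will be obtained from the subject's medical record". It says eGFR will be measured at each standard-of-care visit and makes no such statement for ALT.

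**SAP.** Part 14 names Arm 1 as the only patient group and defines a binary response "with '1' corresponding to peak ALT > 5 x ULN". The SAP lists no between-arm composite.

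**The concern.** A peak or any-time laboratory outcome can occur in the data only if the test is done. Its observed frequency therefore depends on the number and timing of draws as well as on the true rate. Here the guaranteed draws fall in one arm and cluster in the weeks that arm is on G/P.

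With equal true hepatic risk, more short, silent ALT rises would be recorded in Arm 1. The covariates cannot remove this. Footnote 8 operates within a centre: where local chemistry omits liver tests, the Arm 1 recipient gets them by study order and the Arm 2B recipient may not. Adjusting for region does not separate those two subjects.

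Length of follow-up pushes the same way. Arm 1 is followed for 1 year after transplant. Arms 2A and 2B are followed for the longer of 24 weeks after transplant or 1 year after enrollment, so some comparators may contribute only about 24 post-transplant weeks.

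**Working it through.** The plan gives no event rate, power or expected difference for this comparison, so there is no figure to reproduce. The calculations below are for scale only.

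**Inputs**
- Arm 1 draws: treatment weeks 1, 4 and 8. With G/P starting on day 3 (the protocol's target), these are days 10, 31 and 59 after transplant.
- ALT rise: lasts w = 7, 14 or 21 days, with onset uniform over days 4-60 (56 days). Assumed.
- Comparator testing: one ALT every 28 days. Assumed.
- q, the true share of recipients with ALT > 5x ULN, equal in both arms: 5-10%, with 20% as an outer value. Assumed.
- b, the probability of any other composite component, independent of ALT: 0.40. The protocol's risk section (9.4.1) expects about 40% readmission within 30 days, and most admissions meet the SAE definition. 0.80 is used as a second assumed value because delayed graft function, rejection and later SAEs add to it.

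**Step 1: detection**

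In Arm 1 a rise is found if its onset falls within w days before a draw. Onsets before day 4 are outside the window, so the day-10 draw covers only 6 days.

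| w (days) | Arm 1 | Monthly comparator | Gap |
|---|---|---|---|
| 7 | (6+7+7)/56 = 36% | 7/28 = 25% | 6/56 |
| 14 | (6+14+14)/56 = 61% | 14/28 = 50% | 6/56 |
| 21 | (6+21+21)/56 = 86% | 21/28 = 75% | 6/56 |

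The gap is 6/56, or about 11 points, at every duration.

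**Step 2: composite with monthly comparator testing**

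p = b + (1 - b) x q x detection. For 14-day rises:
- b = 0.40, q = 5%: 41.82% vs 41.50%, difference 0.3 points, OR 1.01.
- b = 0.40, q = 10%: 43.64% vs 43.00%, difference 0.6 points, OR 1.03.
- b = 0.80, q = 5% and 10%: differences 0.1 and 0.2 points, OR 1.01 in both.

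For ALT alone at q = 10%, the observed rates are 6.1% and 5.0%, OR 1.23.

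**Step 3: poor comparator detection**

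Arm 1 is now taken to find every rise and the comparator a fraction d. The spurious difference is (1 - b) x q x (1 - d). At q = 10%:

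| d | ALT alone | Composite, b = 0.40 | Composite, b = 0.80 |
|---|---|---|---|
| 0.25 | 7.5 points, OR 4.3 | 4.5 points, OR 1.20 | 1.5 points, OR 1.10 |
| 0.50 | 5.0 points, OR 2.1 | 3.0 points, OR 1.13 | 1.0 point, OR 1.07 |
| 0.75 | 2.5 points, OR 1.4 | 1.5 points, OR 1.06 | 0.5 points, OR 1.03 |

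The outer corner (q = 20%, d = 0.25) gives a composite OR of 1.44 at b = 0.40 and 1.23 at b = 0.80.

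**Step 4: false positives**

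With 30 subjects in Arm 1, an assumed 30 comparators, b = 0.40, q of 5-20% and d of 0.25-0.75, the chance of a significant result against Arm 1 is 2.9% to 10.3%, where 2.5% is nominal. At q = 10% and d = 0.25 it is 5.4%.

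**Section 6.1.8.** Its repeat tests follow a value already above the threshold. They add to Arm 1's draw count but do little to the chance of a first crossing. Footnote 8 carries the asymmetry.

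**The case against.** The strongest reply is that ALT will be drawn in every arm. Section 5.1.1 covers all patients and lists clinical chemistry, Table 8 places ALT within chemistry, and Table 5 itself puts chemistry under standard of care. Footnote 8 is a conditional backstop: at a site that already runs liver tests routinely it adds nothing, and it does not show that any site omits them. Arms 2B1-2B4 are followed at study sites, and ALT > 5x ULN is asked about at Arm 2A study visits. All of this stands, and it limits the size of the bias. It does not give the comparator the guarantee that Arm 1 has.

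A reader might go further and infer that Arm 2A has no scheduled chemistry, because Table 6 shows no chemistry ticks at its routine visits. The table is broken in extraction and lacks ticks for vital signs too, although Section 5.1.7 says these are performed and collected. The empty cells are not evidence.

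A reader might also suppose that 3-7% of otherwise event-free Arm 1 subjects would enter the composite through extra testing. Against monthly comparator testing that needs a true rate of 3/11 = 27% to 7/11 = 64%, which nothing in the documents supports. Otherwise it needs comparators with essentially no ALT draws, contrary to Section 5.1.1.

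Nor would a composite difference by itself read as G/P or HCV liver toxicity. SAEs are likely to dominate the composite, and outcomes are also summarised one by one and by relatedness.

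Finally, Section 8.1 defers analysis details to the SAP, which restricts ALT to Arm 1, and the Synopsis safety text calls these data descriptive. Neither withdraws the regression stated in the Synopsis and Section 8.1.4, and the SAP is a draft summary.

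**Conclusion.** The concern holds as a directional ascertainment bias against Arm 1 in a secondary comparison. It rests on footnote 8 applying to Arm 1 only, the standard-of-care follow-up of Arm 2A, the medical-record source for Arm 2B, and covariates that do not address testing frequency or length of follow-up.

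Its size cannot be derived from the documents. In the composite it is probably small: OR about 1.01-1.03 if comparators have monthly ALT and the true rate is 5-10%, and about 1.2 if three quarters of comparator rises are missed at a 10% rate with b = 0.40. Only a 20% true rate combined with that poor detection takes it further. Where local practice draws liver tests as often as Table 5, it shrinks towards zero. The by-arm ALT percentage has no dilution from SAEs and could be materially distorted.

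The change is worth making because the direction is known, the protocol and SAP already disagree on this outcome, and the remedy costs almost nothing.

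**What to change.** 1. In Section 8.1.4 and the matching Synopsis text, define the composite for the between-arm logistic regression without ALT > 5x ULN, or present the regression with and without it.
2. Report ALT > 5x ULN descriptively by arm, together with the number of ALT draws and the length of post-transplant follow-up per subject.
3. Reconcile the protocol with SAP Part 14, and state in the SAP whether the composite regression is still planned.

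Do not rely on a comparison limited to subjects who happen to have ALT values near weeks 4 and 8. Without guaranteed testing, comparator values at those times may have been drawn for cause, which brings in a selection bias of its own.

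This is a wording change with no added visits or tests. The one downside is that the tested composite has one fewer component; the ALT information is still reported.
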